15.4.2 Injection Site Reactions

The severity of injection site reactions will be graded according to the following scale (semicolon indicates "or" within description of grade:

- Mild: Pain that does not interfere with activity; mild discomfort to touch; <5 cm of erythema or induration that does not interfere with activity
- Moderate: Pain that requires repeated use of non-narcotic pain reliever >24 hours or interferes with activity; discomfort with movement; 5.1 cm to 10 cm erythema or induration or induration that interferes with activity
- Severe: Pain that requires any use of narcotic pain reliever or that prevents daily activity; significant discomfort at rest; >10 cm erythema or induration; prevents daily activity; requires ER visit or hospitalization; necrosis or exfoliative dermatitis.

15.4.3 Evaluation of Causality

Relationship of Adverse Events to Study Drug:

The relationship of AEs/SAEs to study drug will be assessed by the masked investigator and will be a clinical decision based on all available information. The following question will be addressed:

Is there a reasonable possibility that the AE/SAE may have been caused by the study drug? The possible answers are:

Not Related: There is no reasonable possibility that the event may have been caused by the study drug

Page 35 of 58 Version: 3.7.3 2Apr2024 • **Related:** There is a reasonable possibility that the event may have been caused by the study drug

A list of factors to consider when assessing the relationship of AEs to study drug is provided in Appendix B. The investigator should consult the Investigational Brochure, which lists the possible adverse events.

The investigator should justify the causality assessment of each SAE.

15.5 Safety Monitoring

The site investigator will monitor the safety of study subject at his/her site(s) as per the requirements of this protocol and consistent with current Good Clinical Practice (GCP). The sponsor-investigator will monitor the safety data from across all study sites. Safety monitoring will be performed on an ongoing basis (e.g., individual review of SAEs) and on a biannual cumulative aggregate basis by the DSMB.

15.6 External Study Monitor

Westat (Rockville, MD) will serve as the independent study monitor. All on-site monitoring visits are expected to require a maximum of 3 days and will be conducted according to Westat's standard operating procedures (SOPs). The site monitor will perform 100 percent informed consent review, 100 percent review of eligibility and SAE documentation, 30 percent overall source data verification, and 100 percent source data verification for queries.

15.7 Monitoring Table 2

DSMP Requirement	How this Requirement is Met	Frequency	Responsible Party(ies)
Site Monitoring at predetermined intervals: The Principal Investigator has a responsibility to ensure that the study is following all aspects of the protocol.	There should be a standard operating procedure to review data (whether a sample or 100%) at pre-determined intervals to ensure that there is adequate documentation of critical elements such as eligibility criteria. Monitoring is required at the following timepoints (but may be done more frequently): study initiation at least every six months while participants are receiving intervention and annually while participants are in follow-up 	At a minimum, a review is required annually when no one has been enrolled or the study is in long term follow up. Additional interim monitoring at least once every 12-24 weeks based on the site activity, and more as needed, to include the possibility of remote monitoring.	Delegate a responsible party for each requirement below*. Self-assessment is NOT acceptable. An experienced, knowledgeable person who is independent of the study team should serve as monitor. A Contract Research Organization (CRO) may be used. Consult the IRB Office regarding acceptable qualifications for the independent monitor, if not using an outside expert such as a CRO.
Real-time review of participant data during initial data collection.	Follow the Quality management Plan and the Manual of Operating Procedures	Expectation is that this happens every time you obtain information.	Everyone on the study team responsible for primary data collection.
100% review of regulatory files	Based on the site monitoring plan developed by Westat	Reviewed at a minimum of first and close-out visits	Westat
100% review of consent forms	Based on the site monitoring plan developed by Westat	Biannually	Westat
Review of credentials, training records, the delegation of responsibility logs (if applicable)	Included in the regulatory startup package from Westat	Biannually	Westat
Comparison of case report forms (CRF) to source documentation for accuracy and completion	Included in the Manual of Operating Procedures	Biannually	Westat
Review of documentation of all adverse events	Monitoring plan and startup package	Biannually	Westat
Monitoring of critical	Monitoring plan	Biannually	Westat

data points (eligibility, study endpoints, etc.)			
Laboratory review of processing and storage of specimens	Monitoring plan	Reviewed at first and close-out visits and at least biannually	Westat
Assessment of laboratory specimens stored locally	Monitoring plan and startup package	Biannually	Westat
Test article accountability review	Monitoring plan and startup package	Reviewed at first and close-out visits and at least biannually	Westat
Accountability logs, dispensing records, and other participant records	Monitoring plan and startup package	At least biannually	Westat
For FDA regulated	How this Requirement is Met	Timing,	Responsible
studies, the following		frequency, and	Party(ies)
requirements apply:		intensity of monitoring	
Monitoring methods (may include centralized, on-site, and self- monitoring)	Self-monitoring	Annually	Sponsor-Investigator

^{*}For international studies, you are required to engage a CRO that is working in the site country and/or to consult with Emory's legal counsel regarding compliance with the country's clinical research regulations.

16. Provisions to Protect the Privacy Interest of Participants

Each subject will be assigned a unique identifier. Any subject records or data sets transferred to the coordinating study center will contain only the identifier. Patient names or any information which would make the subject identifiable will not be transferred. The subject must be informed that his/her personal study-related data will be used by the study team in accordance with local data protection law. The level of disclosure must also be explained to the subject.

The subject will be informed that their medical records may be examined by Clinical Quality Assurance auditors or other authorized personnel appointed by study Investigators, appropriate IRB/IEC members, and by inspectors from RAs.

17. Informed Consent

The Investigator or his/her representative will explain the nature of the study to the subject in a private setting and answer all questions regarding the study. Patients must be informed that their participation is voluntary. Patients will be required to sign a statement of informed consent and authorization that meets the requirements of 21 CFR 50, local regulations, ICH guidelines, Health Insurance Portability and Accountability Act requirements and the IRB/IEC or study site.

The research record must include a statement that written informed consent was obtained before the subject was enrolled in the study and the date the written consent was obtained. The authorized person obtaining the informed consent must also sign the ICF. Patients must be reconsented to the most current version of the ICF(s) during their participation in the study as deemed appropriate by the overseeing IRB.

A copy of the ICF(s) must be provided to the subject or the subject's legally authorized representative. Patients who are re-screened are required to sign a new ICF.

The ICF will contain a separate section addressing the use of subject samples for future exploratory research. The Investigator or authorized designee will explain to each subject the objectives of the future exploratory research. If a subject withdraws consent to the use of donated biological samples, the samples will be disposed of/destroyed, and the action documented. If samples already have been analyzed at the time of the request, the Investigator will not be obliged to destroy the results of this research.

18. Setting

Research procedures will take place in the clinic of the principal investigators. Patients will be identified from the schedules of the investigators and collaborators.

19. Appendix

Appendix A: Regulatory, ethical and study oversight considerations

A1. Regulatory and ethical considerations

This study will be conducted in accordance with the protocol and with the following:

- Consensus ethical principles derived from international guidelines including the Declaration of Helsinki and Council for International Organizations of Medical Sciences International Ethical Guidelines;
- Applicable International Conference on Harmonization (ICH)/Good Clinical Practice (GCP) Guidelines;
- Applicable laws and regulations.

The protocol, protocol amendments, Informed Consent Form (ICF), Investigator Brochure, and other relevant documents (e.g. advertisements) must be submitted to an Institutional Review Board/Independent Ethics Committee (IRB/IEC) by the Investigator and reviewed and approved by the IRB/IEC before the study is initiated at that site.

Any amendments to the protocol will require IRB/IEC approval before implementation of changes made to the study design, except for changes necessary to eliminate an immediate hazard to study participants.

The Investigator will be responsible for the following:

- Notifying the IRB/IEC of serious adverse events or other significant safety findings as required by IRB/IEC procedures;
- Providing oversight of the conduct of the study at the site and adherence to requirements of 21 CFR, ICH guidelines, the IRB/IEC, and all other applicable local regulations.

A2. Financial disclosure

Investigators and Sub-Investigators will provide accurate financial information as requested to allow for complete and accurate financial certification or disclosure statements to the appropriate Regulatory Authorities. Investigators will provide information on financial interests during the course of the study and for 1 year after completion of the study.

A3. Informed Consent

The Investigator or his/her representative will explain the nature of the study to the subject and answer all questions regarding the study.

Patients must be informed that their participation is voluntary. Patients will be required to sign a statement of informed consent and authorization that meets the requirements of 21 CFR 50, local regulations, ICH guidelines, Health Insurance Portability and Accountability Act requirements and the IRB/IEC or study site.

A copy of the ICF(s) must be provided to the subject or the subject's legally authorized representative.

Patients who are re-screened are required to sign a new ICF.

The ICF will contain a separate section addressing the use of subject samples for future exploratory research. The Investigator or authorized designee will explain to each subject the objectives of the future exploratory research. If a subject withdraws consent to the use of donated

Page 40 of 58 Version: 3.7.3 2Apr2024

biological samples, the samples will be disposed of/destroyed, and the action documented. If samples already have been analyzed at the time of the request, the Investigator will not be obliged to destroy the results of this research.

A4. Data Protection

Each subject will be assigned a unique identifier. Any subject records or data sets transferred to the coordinating study center will contain only the identifier. Patient names or any information which would make the subject identifiable will not be transferred. The subject must be informed that his/her personal study-related data will be used by the study team in accordance with local data protection law. The level of disclosure must also be explained to the subject.

The subject will be informed that their medical records may be examined by Clinical Quality Assurance auditors or other authorized personnel appointed by study Investigators, appropriate IRB/IEC members, and by inspectors from FDA.

A5. Dissemination of Study Data

A description of this clinical trial and summary of results (when available) will be available on http://www.clinicaltrials.gov.

A6. Publication Policy

The results of this study may be published or presented at scientific meetings. If this is foreseen, the Sponsor-Investigator agrees to submit all manuscripts or abstracts to Sanofi before submission. This allows Sanofi to protect proprietary information and to provide comments. Authorship will be determined by mutual agreement and in line with International Committee of Medical Journal Editors authorship requirements.

Appendix B: Factors in Assessing the Relationship of Adverse Events to Study Drug Is there a reasonable possibility that the event may have been caused by the study drug? No:

- Due to external causes such as environmental factors, ESIs or other treatment(s) being administered
- Due to the subject's disease state or clinical condition
- Do not follow a reasonable temporal sequence following the time of administration of the dose of study drug or injection procedure, study procedure, or background treatment, etc.
- Do not reappear or worsen when dosing with study drug or injection procedure, study procedure, or background treatment, etc. is resumed are not a suspected response to the study drug or injection procedure, study procedure, or background treatment, etc. based upon preclinical data or prior clinical data

Yes:

- Could not be explained by environmental factors or other treatment(s) being administered
- Could not be explained by the subject's disease state or clinical condition follow a reasonable temporal sequence following the time of administration of the dose of study drug, etc.
- resolve or improve after discontinuation of study drug, etc.
- reappear or worsen when dosing with study drug is resumed
- are known or suspected to be a response to the study drug based upon preclinical data or prior clinical data detailed in the package insert.

Version: 3.7.3 2Apr2024

NOTE: This list is not exhaustive.

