3.3 Safety Objectives

Safety objective	Endpoint/variable(s)
Assess the safety of dupilumab after sinus	Continual reporting of events of special
surgery	interest (ESIs) and serious adverse events
	(SAEs)
	Physical examination

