Per FDA regulation 312.32, written IND safety reports will be submitted to the FDA by the IND sponsor, for serious, unexpected suspected adverse reactions within 15 calendar days of the sponsor determining that the event qualifies for reporting. If the event is fatal or is deemed to be life threatening, the report will be made within 7 calendar days of receipt of such information. The IND sponsor will also make an assessment of whether the event constitutes an unanticipated problem posing risks to participants or others (UP). This assessment will be provided to the Emory University IRB, which, in turn will make a final determination. If the Emory IRB determines an event is a UP it will notify the appropriate regulatory agencies and institutional officials.

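### Appendix B names ESIs, the trial's own safety endpoint, as an external cause supporting a Not Related rating, and the matching Yes factor omits them

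*Combined protocol and SAP*

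**What the plan says.** Section 15.4.3 asks the masked investigator to rate each adverse event as Related or Not Related, and adds: "A list of factors to consider when assessing the relationship of AEs to study drug is provided in Appendix B". The first group of factors in Appendix B is headed "Is there a reasonable possibility that the event may have been caused by the study drug? No", and its first entry is "Due to external causes such as environmental factors, ESIs or other treatment(s) being administered". The matching entry in the Yes group is "Could not be explained by environmental factors or other treatment(s) being administered". ESIs appear in the first entry and not in the second.

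Appendix B does not expand ESI, and the abbreviation list in the Study Summary has no entry for it. The one expansion is in the safety endpoint row of Section 3.3: "interest (ESIs) and serious adverse events" (the row begins with continual reporting of events of special interest). Section 15.3.3 lists the events themselves under the label AESI. They include anaphylactic and systemic hypersensitivity reactions, keratitis, severe conjunctivitis and symptomatic eosinophilia, and also pregnancy and symptomatic overdose.

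**The concern.** Events of special interest are collected because they may be effects of the drug. Naming them among causes external to the drug contradicts that purpose. The list is also in active use, since Section 15.4.3 sends investigators to it when they rate causality.

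The relatedness label is what is at stake. Under Section 15.3.3, "written IND safety reports will be submitted to the FDA by the IND sponsor, for serious, unexpected suspected adverse reactions". An event judged to have no reasonable possibility of drug causation would not ordinarily count as a suspected reaction. The label also bears on which events the investigator follows up as related to the intervention (Section 15.3). It is part of the serious adverse event (SAE) report that goes to the DSMB Chairperson, and relatedness is one of the three conditions for an unanticipated problem (both in the DSMB Charter, Appendix C).

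**Working it through.** No arithmetic applies: the point does not touch sample size, power or alpha, and the plan states no figure to reproduce. The check sets the passages side by side.

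1. **What the term means.** The only expansion of ESI is in Section 3.3. Equating it with the AESI list in Section 15.3.3 is an inference, because the two abbreviations differ. It is the natural reading: both stand for events of special interest, and nothing else in the protocol fits.

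2. **Whether the two lists agree.** The first No factor names environmental factors, ESIs and other treatments. The first Yes factor names environmental factors and other treatments only. If both describe the same kind of alternative explanation, ESIs are the sole difference, which suggests a stray term.

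3. **Whether No means Not Related.** Section 15.4.3 defines Not Related by the same reasonable-possibility question that heads the Appendix B list, so a No factor feeds directly into that rating.

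4. **What the entry covers when read literally.** It covers an adverse event that is *due to* an ESI. It does not cover the ESI itself. Section 15.3 asks investigators to establish a diagnosis and record that as the event, so a symptom of a hypersensitivity reaction would normally be recorded within the reaction. Hospital admission is a seriousness criterion in Section 15.2.2, not an event to be rated. What remains is a separately recorded event that follows from an ESI; a fracture from a fall during an anaphylactic reaction would be one (my illustration).

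5. **What depends on the label and what does not.**
   - Dependent in part: treatment of a serious unexpected event as a suspected adverse reaction for IND reporting. The 15-day clock in Section 15.3.3 runs from the sponsor's own determination, so the site label is an input and not the decision.
   - Not dependent: SAE notice to the Sponsor-Investigator within 24 hours, whatever the causality (Section 15.3.2).
   - Not dependent: AESI notice to the sponsor within 24 hours, with no causality condition (Section 15.3.3).
   - Not dependent: reporting of all SAEs to the DSMB Chairperson, who forms a separate view on attribution and expectedness (Appendix C).
   - Not dependent: the comparison of cumulative AESI incidence by risk difference (Section 14.11), which has no relatedness filter.

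6. **Whether other text corrects the entry.** None does.

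**The case against.** The strongest reply is that one stray word in a guidance list changes little. Section 15.4.3 makes causality a clinical judgement on all the information, also points to the Investigational Brochure, and requires a justification for each SAE. Appendix B says "NOTE: This list is not exhaustive". Its Yes group also includes events that "are known or suspected to be a response to the study drug based upon preclinical data or prior clinical data detailed in the package insert", which pulls against the stray word.

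Most of this stands, and it limits the reach of the point. Two parts do not fully answer it. A non-exhaustive list can still contain a wrong entry. The counterweight in the Yes group rests on what is already in the package insert, so it is likely to help least with unexpected events, the kind that IND reports concern. The Chairperson's second view is described for SAEs; no passage gives an equivalent second rating for each non-serious event.

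A reader might infer that harm arising from these events drops out of IND safety reporting, or that each case comes down to a 7- or 15-day report or none. The documents do not support that, because the sponsor receives every SAE and decides what qualifies. A reader might also infer that the DSMB and the final report would see drug harm understated. That is not supported for AESI incidence or for SAE notification; at most, tabulations by the investigator's relatedness label could be affected.

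Finally, not every listed AESI points to the drug. Pregnancy in a male participant's partner and overdose with a non-investigational medication are on the list. This argues for judging each event on its merits, and equally against a blanket label of external cause.

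**Conclusion.** The inconsistency is real and sits in text that investigators are told to use. Its effect is narrow: it can bias the site's relatedness label for a separate adverse event that follows from an event of special interest, and through that label it may influence an IND reporting decision. It does not remove any event from expedited notification, DSMB review of SAEs or the AESI analysis. The documents give no basis for counting the events affected. The conclusion assumes that ESI in Appendix B means what Section 3.3 says it means. If another meaning was intended, the term is undefined where it is used and still needs correcting.

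**What to change.** Delete ESIs from the first factor under No in Appendix B, so that it names only environmental factors and other treatments, as the Yes factor does. Use one term, ESI or AESI, in Section 3.3, Section 14.11, Section 15.3.3 and wherever else it occurs. Tell sites of the correction.

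Do not add a sentence saying that a consequence takes the causality rating of the AESI that led to it. With pregnancy on the list, a congenital anomaly could then inherit Not Related from the pregnancy, and the event-by-event judgement in Section 15.4.3 would be overridden.

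The cost is one word deleted, a consistency edit and a site note. Sample size, analysis and treatment are untouched. A few more events may be rated Related.

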Appendix C: Data and Safety Monitoring Board Charter

Data and Safety Monitoring Board (DSMB) Charter

Protocol:

S-I: A randomized, 52-week treatment double-blind, placebo-controlled efficacy and safety study of dupilumab 300 mg every other week after endoscopic sinus surgery in patients with allergic fungal rhinosinusitis (AFRS) on a background therapy with intranasal corticosteroid spray

Version: 3.7.3 2Apr2024

Short:

Add-on Dupilumab for AFRS as Postoperative Therapy (ADAPT)

Office of the Clinical Director

Emory Principal investigator:

Assistant Professor, Rhinology and Skull Base Surgery Division Department of Otolaryngology – Head & Neck Surgery Emory University School of Medicine

TABLE OF CONTENTS DSMB RESPONSIBILITIES......3 DSMB MEMBERSHIP......4 CONFLICT OF INTEREST5 Confidentiality......5 Status Reports (during active enrollment)......8 Unanticipated Problems 8 Communication with the DSMB 9

INTRODUCTION

The Data and Safety Monitoring Board (DSMB) acts in an advisory capacity to the Sponsor-Investigator to review participant safety and study progress for "A randomized, 52-week treatment double-blind, placebo-controlled efficacy and safety study of dupilumab 300 mg every other week after endoscopic sinus surgery in patients with allergic fungal rhinosinusitis (AFRS) on a background therapy with intranasal corticosteroid spray". This study is funded by Sanofi (Paris, FR). The purpose of this document is to outline the charge to the DSMB regarding its responsibilities, composition, and processes for the above-mentioned study. The NIH mandate requires safety oversight and monitoring for all interventional studies to be commensurate with risks, nature, size, and complexity of the study. This Charter is intended to be a living document to be modified at any time.

DSMB RESPONSIBILITIES

Responsibilities of the DSMB are to:

- a) Review the research protocol, Data and Safety Monitoring Plan (DSMP), and informed consent documents, including all proposed revisions.
- b) Evaluate the progress of the study on an ongoing basis, as needed, including periodicassessments of data quality, participant recruitment, accrual and retention, participant risk versus benefit, performance of study sites, and other factors that can affect the outcome.
- c) Consider the impact of factors external to the study when new information, such as scientific or therapeutic developments, becomes available and may affect safety of participants, their willingness to participate in the study or the ethics and conduct thereof.
- d) Review unanticipated problems, serious and non-serious adverse event reports and documentation and make recommendations to the Sponsor-Investigator regarding protection of the study participants.
- e) Assist the Sponsor-Investigator by commenting on any problems with study conduct or performance.
- f) Ensure that the plan for maintaining the confidentiality of the study data and the results by the investigative team is appropriate.
- g) Review and evaluate requests for protocol modifications.
- h) Review accumulating data at the specified intervals, and as appropriate, and make a recommendation to continue, terminate or modify the study based on observed benefit or harm.

The Sponsor-Investigator may discharge one or all of the DSMB members from their duties when:

a) "A randomized, 52-week treatment double-blind, placebo-controlled efficacy and safety study of dupilumab 300 mg every other week after endoscopic sinus surgery in patients with allergic fungal rhinosinusitis (AFRS) on a background therapy with intranasal corticosteroid spray" is complete;

- b) a member is not able to fulfill the DSMB responsibilities as outlined in the Charter;
- c) the Sponsor-Investigator no longer has oversight responsibilities of the study and/or;
- d) a member is found to have a Conflict of Interest (COI).

Additionally, a DSMB member may resign at any point during the study when:

- e) a member is not able to fulfill the responsibilities, as outlined in the Charter;
- f) a member believes a Conflict of Interest (COI) exists.

DSMB MEMBERSHIP

The DSMB consists of four members who have been appointed by the Sponsor-Investigator. Three members will constitute a quorum for voting. Membership consists of persons independent of the study who have no financial, scientific, or other conflicts of interest with the Principal Investigator (PI) or any Co-Investigators.

The DSMB includes experts in or representatives from the fields of Otolaryngology, Allergy/Immunology and Biostatistics.

Individuals with additional expertise may be invited to participate as non-voting members in the DSMB meeting in certain situations. Non-voting members must also be independent of the study and have no financial, scientific, or other conflicts of interest with the PI or any Co-Investigators.

DSMB Chairperson

The DSMB Chairperson is appointed by the Sponsor-Investigator and confirmed by DSMB vote at the first meeting. The DSMB members must provide a full consensus vote when electing the DSMB Chairperson. The Chairperson is responsible for overseeing the meetings, working with the Sponsor-Investigator and/or the Executive Secretary (ES) to develop the agenda, and summarizes all DSMB recommendations. The Chairperson is the primary contact person for the DSMB.

[name] has been appointed as the DSMB Chairperson.

DSMB Safety Officer

The DSMB Safety Officer (SO) is appointed by the DSMB Chairperson and confirmed by DSMB vote at the first DSMB Meeting. The DSMB must provide a full consensus vote when electing the DSMB Safety Officer. The Safety Officer is the DSMB contact person for expedited reports (e.g., SAEs, protocol violations, and unanticipated problems). Expedited reports must be reported to the DSMB Safety Officer and Executive Secretary within 48 hours of the study personnel receiving notification of the event. The Safety Officer provides an assessment of the action taken by the investigative team and makes a recommendation as to whether further action should be taken (e.g. collection of follow up information or a full DSMB discussion).

While the FDA requires expedited reporting of Serious Adverse Events (SAEs) through the Executive Secretary, the Safety Officer does not provide real time assessment of SAEs. It is the responsibility of the Sponsor-Investigator to provide real time assessment and take the necessary, immediate action with regard to participant safety.

Version: 3.7.3 2Apr2024

[name] has been appointed as the DSMB Safety Officer.

DSMB Executive Secretary

The Executive Secretary (ES) drafts meeting agendas in consultation with the Sponsor-Investigator, DSMB Chairperson, and program staff. The agenda is sent to the full DSMB and the Sponsor-Investigator for input. The ES coordinates the DSMB meetings and conference calls and provides logistics support and meeting summaries. The ES will transcribe the meeting recommendations and minutes and will distribute them to the Sponsor-Investigator, DSMB Chairperson and members. The ES is the primary contact point for DSMB communication with the Sponsor-Investigator.

[name] has been appointed as the DSMB Executive Secretary.

CONFLICT OF INTEREST

Individuals invited to serve on the DSMB as must disclose any potential conflicts of interest, whether real or perceived, to the Sponsor-Investigator. Conflicts of interest can include, but are not limited to, professional, proprietary, and miscellaneous interests. Any real or potential conflicts that develop during a member's tenure on a DSMB must be disclosed for the Sponsor-Investigator consideration at the time the potential conflict is realized. In addition, written documentation attesting to an absence of conflict of interest is required annually.

Confidentiality

Each member of the DSMB must sign a statement of confidentiality annually. All materials, discussions, and proceedings of the DSMB are completely confidential. Members and other participants in DSMB meetings are expected to maintain confidentiality.

BOARD PROCESSES

Prior to commencement of recruitment, the study team drafts or revises study materials (protocol, DSMP and report templates, and any other materials required for the DSMB's review). The study team delivers relevant materials to the ES, who facilitates the review process with the DSMB.

- a) Upon completion of the initial review, the DSMB members are to send the ES their comments for consideration. Accepted comments and recommendations are sent to the Sponsor-Investigator for review.
- b) ES concurrently schedules an introductory teleconference between the Sponsor-Investigator and DSMB. All discussions are confidential.

The first meeting is held either by teleconference or in-person before initiation of the study to discuss the materials and whether the study is ready to commence, establish guidelines for monitoring and determine the format for future meetings. The Sponsor-Investigator and ES prepare the agenda to 1) review the study materials, 2) appoint the DSMB Chairperson and Safety Officer, 3) discuss the plan and timing for safety monitoring 4) make recommendations to initiate the study and/or modify the study materials and 5) review the charter. During the initial DSMB meeting, a representative provides a training session outlining the board process and DSMB procedures for all meeting participants (DSMB members, study staff and coordinator).

Version: 3.7.3 2Apr2024

Reports for both the open and closed sessions should be established at the initial DSMB meeting,

Page 47 of 58 IRB Form BIO 03152021 although changes throughout the study may be requested by the DSMB. In addition, the DSMB members will vote to recommend commencement of the study.

Routine meetings of the DSMB are held two times a year via video conference call. Attendance at all meetings is highly critical for all DSMB members. Each DSMB member is specifically selected for his/her expertise and thus the member's consistent participation ensures rigorous monitoring throughout the course of the study. The DSMB coordinator also attends all DSMB meetings and meeting sessions to provide logistical support and transcribe meeting summaries. Meetings are to be closed to the public because of participant confidentiality considerations.

All DSMB discussions are confidential. An ad hoc meeting of the DSMB may be called at any time by the Chairperson should ethical or patient safety issues arise. The suggestion to convene an ad-hoc meeting should be transmitted to the ES, who will notify the Sponsor-Investigator and DSMB coordinator. Depending on the situation, this meeting may include the Chairperson alone, a quorum of the DSMB, or the full DSMB.

Meeting Format

DSMB meetings consist of open and closed sessions. Discussion held in all sessions is confidential. All invited meeting participants, including the investigators, institution staff and the ES, may attend **open sessions**. All sessions are normally attended by a minimum of three voting DSMB members. The Sponsor-Investigator and the study statistician must be present. The number of coordinating staff attending DSMB meetings should be minimized and only include experienced and trained staff. Other staff may be invited to attend only when appropriate. Open session discussion focuses on the conduct and progress of the study, including patient accrual, protocol compliance, and problems encountered. **Unmasked data are not presented in the open session.**

The closed session is normally attended by the DSMB members, the ES, and the unmasked study statistician or unmasked study team designee. If necessary, all unmasked safety data and efficacy data by treatment group may be presented during the closed session. The DSMB determines in advance, in what format it wishes to see the data during the closed session. The discussion during the closed session is completely confidential, and thus attendance is limited to the members listed in this section, based on their safety monitoring and oversight roles and responsibilities. The DSMB remains unmasked at all times during the closed session.

If necessary, an **open session** may be called following the closed session to clarify any questions that arise from the DSMB. A second **closed session** may also be held, if needed.

Ad-hoc meetings may be held at any time should ethical or safety issues arise. The suggestion to convene an ad-hoc meeting should be transmitted to the ES, who will notify the Chairperson.

Each meeting, whether routine or ad-hoc, must include a recommendation made by a formal DSMB majority to initiate, continue, place on hold or to terminate the study. The decision is ultimately made by the Sponsor-Investigator and sponsoring institution IRB, taking into consideration the recommendation of the DSMB. The vote may be postponed until further information is acquired. Should the DSMB decide to issue a termination recommendation, the full DSMB must vote. In the event of a mixed vote, majority vote will rule and a minority report will be appended.

Specific recommendations will be transmitted in writing to the Sponsor-Investigator within 7 days of meeting completion.

Meeting Materials

DSMB report templates are prepared by the study staff, typically the statistician and/or the data coordinating center in consultation with the Sponsor-Investigator, to be reviewed by the DSMB members at the first meeting. Additions and modifications to the reports can be requested at any time throughout the study. The reports list and summarize safety data, as relevant, and describe the status of the study. All meeting materials must be sent to the ES at least two weeks prior to the meeting for distribution to the DSMB. The ES distributes study materials via the HIPPA compliant, central study data repository (Microsoft OneDrive, Redmond WA). Access will be limited to DSMB members and trained staff. Hard copies of the materials may be sent via express mail to DSMB members at their request. Materials are divided into two parts if requested: Part 1 contains open session materials, which may be shared with the study staff and meeting participants and referenced during any session of the meeting; and Part 2 contains closed session materials, which may contain sensitive or unmasked data and should be discussed in closed sessions only.

Part 1 – Open session materials include administrative reports by study site that describe patients screened, enrolled, completed, and discontinued, as well as baseline characteristics of the study population. Listings and summaries of adverse events and serious adverse events, along with any other information requested by the DSMB may also be in the open session report, but none of the data should be presented in an unmasked manner.

Part 2 – Closed session materials may contain safety data in aggregate, by masked treatment group (A/B presentation), by unmasked treatment group, or in other formats as requested by the DSMB. The closed session reports are confidential. Printed copies of the closed reports should be destroyed immediately following the meeting.

It is important that access to outcome data, when necessary, be limited to the study statistician and/or unmasked study team designee and the DSMB to protect the study from bias in patient entry and/or evaluation. Any unmasked study personnel should be pre-designated.

Meeting Recommendations

